### **8.1.3.3            Pregnancy Test**

All female subjects of child-bearing potential will be tested using a urine pregnancy test for beta-human chorionic gonadotropin. Country-specific mandates may require additional pregnancy testing prior to each infusion.

All female subjects of child-bearing potential must have a negative urine pregnancy test. If the urine test cannot be confirmed as negative, a serum pregnancy test will be required. This pregnancy test must be negative for the subject to be eligible ([Section 4.1.1](#)).

### **8.1.3.4            Vital Signs**

Vital signs measurement will include blood pressure (systolic and diastolic) and pulse rate according to site's standard practices. Blood pressure and pulse rate will be measured after the subject has rested. Pulse rate will be counted and adjusted per minute or measured with an automatic blood pressure monitor.

### **8.1.3.5            Parvovirus Testing**

Samples will be collected from all randomized subjects at Visit 2 (Day 1; before infusion 1) and Visit 6 (Day 29), and will be stored for up to 1 year after completion of the clinical study report or for the duration permitted by national or local regulations for routine testing or safety surveillance. Nucleic acid testing and serology (parvovirus B19) will be performed using complete samples (at all timepoints indicated in [Schedule of Assessments](#)) from approximately 300 randomly selected subjects (approximately 150 CSL112 and 150 placebo) to evaluate changes from baseline (ie, evidence of seroconversion or infection) for parvovirus B19.

### **8.1.3.6            Immunogenicity Testing**

Immunogenicity testing will be performed using blood samples from approximately the first 600 subjects (approximately 300 CSL112 and 300 placebo), and results will be provided to the

IDMC for review ([Section 3.7.1](#)). If no immunogenicity signal is observed in the CSL112-treated subjects, the IDMC can recommend that no further samples be assayed for immunogenicity. Samples will continue to be collected from all randomized subjects and will be stored for up to 1 year after completion of the clinical study report or for the duration permitted by national or local regulations for routine testing or surveillance as immunogenicity testing is part of evaluation for a serious hypersensitivity reaction.

In the event that a subject experiences an SAE of hypersensitivity, or there is suspected angioedema during infusion of investigational product, the subject's blood samples taken at baseline and at the time of the serious hypersensitivity reaction will be analyzed for the presence of binding antibodies specific to CSL112 and apoA-I.

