- K:** Local laboratory values obtained as part of standard of care testing for the index acute myocardial infarction event and before obtaining written informed consent should be used to determine study entry and eligibility for infusion 1. However, if results (for ALT, total bilirubin and / or serum creatinine) are not available, then a blood sample must be obtained for the local laboratory testing.
- L:** **For subjects who received infusion 1 of investigational product  $> 12$  hours and  $< 48$  hours after IV contrast administration:** local laboratory serum creatinine value must be obtained before the infusion for comparison with the local laboratory baseline value and reviewed by the investigator. A blood sample for local laboratory testing to assess dosing eligibility for infusion 2 should not occur earlier than 72 hours following the infusion 1.
- M:** During study conduct, the Independent Data Monitoring Committee (IDMC) may make a recommendation to permit discontinuation of blood sampling at Visit 3 and Visit 4 for local laboratory and / or central laboratory biochemistry testing. If the IDMC so recommends, study investigators will be notified by the Executive Committee chairperson that these routine laboratory assessments are no longer required and eligibility for all subsequent infusions is to be based on clinical assessment (ie, starting with infusion 2 / Visit 3).
- N:** Blood sample is to be taken before the start of infusion. This blood sample must be sent to the central laboratory for study analysis purposes.
- O:** Blood samples are to be collected from all subjects at baseline and Visit 6 (Day 29). Immunogenicity testing will be performed using samples from approximately the first 600 subjects (approximately 300 CSL112 and 300 placebo) and oversight will be provided by the IDMC ([Section 8.1.3.6](#)).
- P:** Blood samples are to be collected from all subjects at baseline and Visit 6 (Day 29). Nucleic acid testing and serology (parvovirus B19) will be performed using samples from approximately 300 randomly selected subjects (approximately 150 CSL112 and 150 placebo).
- Q:** Future biomedical research testing includes samples collected at baseline that are intended for storage and / or future analyses (eg, pharmacogenomics).

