### **8.1.3.1.1 Adverse Events of Special Interest**

#### **8.1.3.1.1.1 Hypersensitivity**

In the event that a subject experiences an SAE of hypersensitivity, or there is suspected angioedema during infusion of investigational product (as defined in [Section 9.1.2](#)), the current infusion and all subsequent infusions must be immediately discontinued. The subject must receive immediate medical assessment and indicated supportive management per the institutional standard of care.

- Additional assessments are to be performed as outlined below. A follow-up is required until resolution of the event. The following assessments should be performed: Collect blood samples for complete blood count with differential ([Table 3](#)), levels of quantitative immunoglobulins (immunoglobulins G, M, E, and A), and presence of anti-IgA antibodies.
- A blood sample for immunogenicity testing will be taken as close as possible to the event and tested for anti-CSL112 and anti-apoA-I antibodies.
- The subject should be re-queried to confirm the absence of a history of allergy to soy or peanuts.
- Pertinent positives and negatives should also be assessed and documented in the source document and eCRF including but not limited to: rash, swelling, hives, itching, shortness of breath, wheezing, stridor, and involvement of the mucous membranes.
- Relevant physical examination findings should also be documented (eg, maculopapular rash, swelling of the face or oropharynx, wheezing, etc.).

Any hypersensitivity reaction should be recorded as an AE ([Section 9.6.1](#)).

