### **8.5.4 Early Termination Visit**

Subjects who prematurely discontinue infusion(s) of investigational product are to be assessed at Visit 6 / Early Termination Visit as soon as possible after discontinuation of investigational product. Refer to [Sections 4.3.1](#) and [4.3.3](#) for definition of discontinuation of treatment and / or subject withdrawal from study, respectively, and [Sections 4.3.4](#) and [4.3.5](#) for follow-up procedures.

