Blood samples drawn from approximately the first 600 subjects (approximately 300 CSL112 and 300 placebo) or in the event of a serious hypersensitivity reaction will be assayed to detect the presence of binding antibodies to CSL112 and apoA-I. Samples from 300 subjects who receive CSL112 will provide a 95% probability of observing at least 1 positive result if the underlying rate is 1/100 (ie, 1%). If no immunogenicity signal is observed in CSL112-treated subjects, the IDMC chair may recommend that no further samples be assayed although samples will be collected from all enrolled subjects at baseline and Visit 6 and stored. The IDMC may also recommend continued assay of immunogenicity samples in an additional subset of subjects based on other safety concerns whether or not immunogenicity signal is observed. The number (%) of subjects with positive results for binding antibodies will be presented.

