The non-inferiority assessment will serve as a minimum criterion for a potential IDMC decision to discontinue routine assessments of renal function prior to infusions 2 and 3. Prior to a decision to discontinue routine assessments of renal function at infusions 2 and 3, the IDMC will also utilize clinical judgment, considering the summary of results for the subgroups outlined above. The IDMC will also use clinical criteria and will review adverse events (AEs) that are related to acute kidney injury, defined as AEs with a MedDRA

Preferred Term included in the Acute Renal Failure narrow Standardized MedDRA Query (SMQ). Prior to any decision, the IDMC will also apply medical judgment to assess severity, reversibility and a change to the benefit-risk balance. After this planned interim renal evaluation, the IDMC will have the option to recommend discontinuing or continuing renal assessments prior to infusions 2 and 3 in the overall study population or in certain subgroups of either renal function (such as moderate renal impairment) or time interval between contrast administration and administration of IP. For example, if data are insufficient in a certain subgroup, the recommendation can be appropriately tailored to ensure adequate safety monitoring in all subgroups of subjects.

Blood samples drawn from the first 600 subjects (approximately 300 CSL112 and 300 placebo) or in the event of a serious hypersensitivity reaction or any event of angioedema will be assayed to detect the presence of binding antibodies to CSL112 and apoA-I. Samples from 300 subjects who receive CSL112 will provide a 95% probability of observing at least 1 positive immunogenicity result if the underlying rate is 1/100 (ie, 1%). The number (%) of subjects with positive results will be presented. The IDMC may request that additional samples be assayed if warranted by the results.

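### After a serious hypersensitivity reaction the protocol requires antibody assay only at baseline and at the event, so a response that develops later is not looked for by default.

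*Protocol*

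**What the plan says.** **Reaction work-up.** Protocol 8.1.3.6 names two samples for assay after a serious adverse event of hypersensitivity or suspected angioedema during infusion: the "blood samples taken at baseline and at the time of the serious hypersensitivity reaction will be analyzed for the presence of binding antibodies". Protocol 8.1.3.1.1.1 says when the second is drawn: "A blood sample for immunogenicity testing will be taken as close as possible to the event and tested for anti-CSL112 and anti-apoA-I antibodies". It lists no later immunogenicity draw.

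**Routine plan.** Note O to the Schedule of Assessments states: "Blood samples are to be collected from all subjects at baseline and Visit 6 (Day 29"). It limits assay to a first cohort: "Immunogenicity testing will be performed using samples from approximately the first 600 subjects (approximately 300 CSL112 and 300 placebo").

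**Storage.** Protocol 8.1.3.6 states: "Samples will continue to be collected from all randomized subjects and will be stored for up to 1 year after completion of the clinical" (here the sentence goes on to name the study report, with what regulations allow as the alternative limit). The reason given is that antibody testing belongs to the evaluation of a serious hypersensitivity reaction.

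**Further assays.** Protocol 10.3.6.2: "The IDMC may also recommend continued assay of immunogenicity samples in an additional subset of subjects based on other safety concerns", whether or not a signal has been seen. SAP 4.6.1.2: "The IDMC may request that additional samples be assayed if warranted by the results". Both sections also provide for assay after a serious hypersensitivity reaction, without naming time points.

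**Visit 6 after a reaction.** Protocol 8.1.3.1.1.1 ends all infusions. Under Protocol 8.5.4, subjects who stop early "are to be assessed at Visit 6 / Early Termination Visit as soon as possible after discontinuation of investigational product". Protocol 4.3.1 adds that if the stop occurs at a scheduled visit, the Visit 6 assessments replace that visit.

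**Reporting.** SAP 11.7.1 counts subjects positive for binding antibodies and summarizes reaction samples apart from routine ones.

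**The concern.** Day 29 is the only post-exposure time point at which the routine plan tests for antibodies. For subjects with a serious reaction, the named pair of samples leaves that time point out. If the reaction comes at infusion 1, baseline and event samples both sit on or about the first day of exposure. They can show antibody that was already there, but they are poorly placed to show antibody formed in response to the product.

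These are also the subjects in whom antibody formation is of most interest. The Visit 6 sample is kept partly for this purpose, yet the list of samples to be analyzed does not include it. The separate reaction summary in SAP 11.7.1 could then consist, for most such subjects, of results with no post-reaction information. A reader could take a negative entry there to mean more than it does.

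**Working it through.** **1. The plan's own figure.** Protocol 10.3.6.2 and SAP 4.6.1.2 give a 95% probability of at least one positive among 300 CSL112 subjects if the true rate is 1%. Check: 1 − 0.99^300 = 0.951. The figure reproduces. It describes the routine cohort, and the present point does not change it.

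**2. Share of subjects whose Visit 6 sample is assayed by rule.** Inputs: 600 subjects (note O); planned enrollment 17,400, range 15,000 to 20,600 (Protocol 10.1.2).

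| Enrolled | In routine cohort | Outside it |
|---|---|---|
| 15,000 | 600/15,000 = 4.0% | 96.0% |
| 17,400 | 600/17,400 = 3.4% | 96.6% |
| 20,600 | 600/20,600 = 2.9% | 97.1% |

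For about 96% to 97% of subjects, a reaction triggers no assay of the Visit 6 sample unless the IDMC extends testing.

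**3. Position of the samples by infusion.** The nominal infusion days are 1, 8, 15 and 22 (Protocol 3.1). The baseline sample is taken before infusion 1. The table takes a reaction on the day of infusion.

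| Reaction at | Event sample, days after first exposure | Visit 6 if held early, days after reaction | Sample kept at Day 29, days after reaction |
|---|---|---|---|
| Infusion 1 (Day 1) | 0 | from 0 | 28 |
| Infusion 2 (Day 8) | 7 | from 0 | 21 |
| Infusion 3 (Day 15) | 14 | from 0 | 14 |
| Infusion 4 (Day 22) | 21 | from 0 | 7 |

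The third column starts at 0 because Protocol 4.3.1 lets the Visit 6 assessments replace the visit at which dosing stops, and 8.5.4 asks for them promptly. Two things follow. The gap is widest for infusion 1 and narrows for later infusions. And adding the Visit 6 assay alone would not close it, because that sample can coincide with the event. This last point also applies to reaction cases inside the first 600.

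**4. Number of subjects.** The documents give no rate of serious hypersensitivity for this trial. Assume 0.05% to 0.5%:

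- 17,400 × 0.0005 = 8.7, about 9 subjects
- 17,400 × 0.005 = 87 subjects

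These counts cover both arms. With 1:1 allocation and equal rates, half of them, about 4 to 44, received CSL112.

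**5. The texts side by side.** Protocol 8.1.3.6 names two samples; Protocol 10.3.6.2 and SAP 4.6.1.2 name none. The triggers also differ. Protocol 8.1.3.6 uses a serious hypersensitivity event or suspected angioedema during infusion, Protocol 10.3.6.2 a serious hypersensitivity reaction only, and SAP 4.6.1.2 a serious hypersensitivity reaction or angioedema of any kind.

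**The case against.** The best defence is that the named pair fits its purpose. Protocol 8.1.3.1.1.1 describes an event work-up: blood count, immunoglobulins, anti-IgA antibodies, allergy history, event sample. Baseline and event samples address whether antibody was present when the reaction happened. Antibody that first appears afterwards cannot explain that reaction, and the subject receives no more infusions. This stands as a reason for having the two samples; it does not show that a third would be uninformative. It is also fair that event samples at infusions 2 to 4 follow roughly one to three weeks of exposure, and that a serious hypersensitivity event need not fall on an infusion day.

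The second defence is that nothing is lost: samples are stored, and the IDMC can have more assayed. That is correct, and it reduces the point to a missing default instruction. But the route is discretionary, and negative results from early samples are unlikely to prompt its use.

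Three stronger readings are tempting, and the documents do not support them:

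- *A later response cannot be seen.* Stored samples, the IDMC's powers (Protocol 3.7.1 and 10.3.6.2, SAP 4.6.1.2) and routine testing of the first 600 all contradict this.
- *The IDMC's oversight of immunogenicity would rest on negatives from reaction cases.* It rests mainly on the first 600 subjects, and SAP 11.7.1 keeps reaction samples separate from routine ones.
- *Infused apoA-I in the circulation compromises the event sample.* Protocol 3.3.2 reports a 2-fold elevation of apoA-I, but neither document says anything about assay interference.

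**Conclusion.** The concern holds as a gap in the default instructions. After a serious hypersensitivity reaction, or suspected angioedema during infusion, the protocol requires assay at baseline and at the event only. For about 96% to 97% of subjects no rule adds the Visit 6 sample, and early discontinuation can bring that sample forward to the event itself. A response that develops after the reaction is therefore not looked for unless someone asks, most clearly after a reaction at infusion 1.

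The size is small: about 9 to 87 subjects in both arms together, resting wholly on the assumed rate of 0.05% to 0.5%. The documents give no time course for antibody formation, so they cannot show how long after exposure a sample must be taken. Day 29 is used here only because the protocol itself chose it for routine testing. The point concerns descriptive safety reporting alone and has no bearing on sample size, power, alpha or the efficacy endpoints.

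**What to change.** - **Protocol 8.1.3.6 and 8.1.3.1.1.1:** state that the baseline, event and Visit 6 immunogenicity samples are all assayed in every subject who meets the reaction trigger.
- **Timing:** for these subjects, keep the Visit 6 immunogenicity sample at or near Day 29 when the Early Termination Visit is held sooner. Only this blood sample is affected; the other assessments of that visit stay as they are.
- **Protocol 10.3.6.2, SAP 4.6.1.2 and SAP 11.7.1:** align them with 8.1.3.6 on which samples and which trigger apply.
- **SAP 11.7.1:** report the post-reaction sample separately from the event sample, with its study day, so that an early Visit 6 sample is recognizable as such.

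The cost is one extra assay per reaction case, about 9 to 87 under the assumed rate, and fewer to the extent that cases fall within the first 600. Some subjects would need a separate Day 29 draw. They remain in follow-up under Protocol 4.3, 4.3.1 and 4.3.4, but some may be followed by telephone and give no sample. Where Day 29 has already passed, the stored Visit 6 sample can still be assayed within the retention period.

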## **8.1.4 Other Assessments**

### **8.1.4.1 Quality of Life Questionnaire**

The EQ-5D-3L is a standardized measure of health status that provides a simple, generic measure of health for clinical and economic appraisal. The questionnaire, which is designed for self-completion by respondents, is applicable to a wide range of health conditions and treatments [[EuroQol Group, 1990](#)]. The questionnaire is to be completed at Visits 1 and 8.

The EQ-5D-3L consists of 2 parts:

- A descriptive profile, comprising the following 5 dimensions: mobility, self-care, usual activities, pain / discomfort, and anxiety / depression. Subjects rate each dimension based on 3 levels of severity (ie, no problems, some problems, extreme problems).
- A vertical, visual analog scale (VAS), on which the subject rates their overall health from 'Best imaginable health state' to 'Worst imaginable health state'.

### **8.1.4.2 Lifestyle Adherence Assessment**

Adherence to guidelines regarding diet and lifestyle restrictions, physical activity and / or cardiac rehabilitation, and tobacco smoking cessation will be assessed at Visit 8 (Day 90), Visit 9 (Day 180), and the EOS Visit (Day 365) (see [Section 7.4](#)).

## **8.1.5 Pharmacokinetic / Pharmacodynamics Assessments**

Blood samples from randomized subjects at selected sites, who provide signed informed consent for PK and PD blood sample collection, will be collected at time points listed in the [Schedule of Assessments](#) for determination of the PK parameters of CSL112 through analysis of apoA-I and PC plasma concentrations and PD analyses of lipid biomarkers (cholesterol

efflux), respectively. Sample analysis will be conducted as detailed in the study reference manuals.

## **8.2 Blood Samples**

Detailed information on the estimated volume of blood to be sampled for each assessment and / or by visits will be available in the informed consent form (ICF) and study reference manuals. Repeat or unscheduled blood samples may be taken for safety reasons or for technical issues with the samples. Refer to the study reference manuals for details about the collection, storage, handling, and processing of blood samples.

## **8.3 Retention of Samples for Future Biomedical Research**

Retention samples including whole blood will be obtained at time point(s) specified in the [Schedule of Assessments](#) for future biomedical research (FBR), including for genomic use, from consenting subjects. Retention samples will be stored and will be destroyed within 10 years after completion of the clinical study report, or for the duration permitted by national or local regulations. Refer to the study reference manuals for further details about the storage and destruction of retention samples.

Research for biomedical testing is to address emergent questions not described elsewhere in the protocol and will only be conducted on a subset of appropriately consented subjects.

Research may be done to explore and identify biomarkers that inform the scientific understanding of the disease and / or therapeutic treatment. The overarching goal is to use the information to understand the risk and progression of the disease of interest, and to develop safer, more effective drugs and / or to ensure the correct dose of drug at the correct time. Future biomedical research testing including samples intended for storage and / or future analyses (eg, archival blood sample) will be collected at time point(s) specified in the [Schedule of Assessments](#).

The decision to assess additional biomarkers from an archival blood may be made by the Executive Committee with input from the Steering Committee, and based on the latest available information on the utility of such measurements. These analyses, including genotypic analysis, may be used for future planning and / or exploratory analyses.

## **8.4 Concomitant Therapies**

All drugs and / or procedures currently being administered to a subject at the time of signing informed consent, and which continue to be taken in addition to investigational product

---

during the study, are regarded as concomitant therapies and must be documented as such in the eCRF. Refer to [Sections 7.2](#) and [8.1.1.3](#) for detailed instructions.

## 8.5 Visit Schedule

The timing and frequency of the study visits, including assessment time windows, are presented in the [Schedule of Assessments](#).

### 8.5.1 Visit 1 (Screening)

All subjects must provide written informed consent before any study-specific assessments or procedures are performed. Written informed consent is not required for assessments or procedures performed according to standard of care (eg, for diagnosis or treatment); results from such assessments may be used in the determination of study eligibility.

Subjects will be assessed for eligibility at screening (Visit 1). Screening / eligibility assessment should occur before or on the day of hospital discharge. Before infusion 1 of investigational product is administered, the subject must be clinically stable and meet all of the inclusion and none of the exclusion criteria ([Section 4.1](#)). Hepatic and renal eligibility must be confirmed by the investigator and there must be no suspicion of AKI ([Section 4.2.1](#)).

Subjects who complete all of these assessments and who fulfill all eligibility criteria (ie, eligible subjects) will be enrolled into the study. If the subject is not eligible for the study, the subject information and primary reason for screen failure must be entered in the IRT.

Screening and randomization of subjects may occur on the same day (Day 1 of the Active Treatment Period) provided that the minimum time window after FMC for the index event is met. All tests and procedures that are required to be performed to determine subject eligibility (ie, screening and randomization) must be performed with enough time to administer the investigational product within this timeframe. If angiography is planned for treatment of the index MI, randomization must occur after the procedure has been performed and stability of serum creatinine confirmed at least 12 hours after IV contrast administration.

The following procedures will be conducted and documented at the Screening Visit:

- Informed consent.
  - All subjects must provide written informed consent before any study-specific assessments or procedures are performed. Written informed consent is not required for assessments or procedures performed according to standard of care (eg, for

diagnosis or treatment); results from such assessments may be used in the determination of study eligibility.

- Informed consent for FBR (optional).
- Medical and surgical history.
- Prior / concomitant medication review.
- Review of inclusion and exclusion criteria.
- IRT subject registration and randomization (if eligible).
  - If the subject is not eligible for the study, the primary reason for screen failure must be entered in the IRT system.
- Pregnancy test (if applicable).
- Demography (year of birth, years of age, sex, race, and ethnicity).
- Height.
- Vital signs.
- Directed physical examination.
- Body weight.
- Blood sample for local laboratory testing (ALT, total bilirubin, and serum creatinine to confirm infusion eligibility), unless already collected as part of standard of care.
- AE / SAE monitoring.
- EQ-5D-3L questionnaire.

